9.9 Sample Size and Power Calculations

9.9.1 Immunogenicity Analyses

In Phase 1, approximately 90 participants will be enrolled, with approximately 30 participants in each of the 3 vaccination groups.

In Phase 2, Approximately 500 participants will be enrolled, with approximately 250 participants in each of the 2 vaccination groups. Assuming 90% evaluability (approximately 225 participants per group), there is 98.7% power to declare primary noninferiority to PNEUMOVAX™23 for the common serotypes and 99.2% power for superiority (ie, statistically significantly greater) for the unique serotypes based on OPA GMT ratios. The overall estimate of power for the primary hypothesis, as the product of the powers for the set of noninferiority hypotheses and the set of superiority (ie, statistically significantly greater) hypotheses, is 98%. This sample size also provides adequate power for the secondary hypotheses. Specifically, there is 87% power for the secondary noninferiority hypothesis and 92% power for the secondary superiority (ie, statistically significantly greater) hypothesis. The overall power for the secondary hypotheses is 80%. The sample size and power calculations are based on the following assumptions:

- The standard deviation of natural log-transformed OPA assay and IgG results are 2.2 and 1.73, respectively. These assumptions are based on observations from previous studies with PNEUMOVAX™23.
- For the common serotypes, the assumed true geometric mean ratios of OPA GMTs and IgG GMCs are 1.
- For the unique serotypes, the assumed true geometric mean ratios of OPA GMTs and IgG GMCs are 3 and 2, respectively.
- 90% evaluability rate (approximately 225 participants per group).

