6.3 Measures to Minimize Bias: Randomization and Blinding

6.3.1 Intervention Assignment

In Phase 1, intervention allocation/randomization will occur centrally using an IRT system. There are 3 study intervention arms. Participants will be assigned randomly in a 1:1:1 ratio to receive either pPCV-1, pPCV-2, or PNEUMOVAX™23.

In Phase 2, intervention allocation/randomization will occur centrally using an IRT system. There are 2 study intervention arms. Participants will be assigned randomly in a 1:1 ratio to receive either pPCV or PNEUMOVAX™23.

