8.2.2 Pneumococcal Electrochemiluminescence (PnECL)

The Sponsor has developed and optimized a multiplex, ECL-based detection method for the quantitation of IgG serotype-specific antibodies to PnP serotypes contained in pPCV. The PnECL v2.0 assay is based on the Meso-Scale Discovery technology, which employs disposable multi-spot microtiter plates. The benefits of the ECL multiplex technology over the prior enzyme-linked immunosorbent assay methodology include speed, equivalent or better sensitivity, increased dynamic range, the ability to multiplex, and reduction in required serum sample and reagent volumes. The measurement of immune responses to the serotypes contained in pPCV is performed using an assay format consisting of 3 groups of 8, 9, and 7 serotypes each. The PnECL v2.0 assay for pPCV will be qualified. The qualification studies will evaluate various performance parameters of the assay including precision, ruggedness, relative accuracy/dilutional linearity, and the limit of detection of the assay.

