GMFRs from prevaccination to 30 days postvaccination for both OPA and IgG responses	Descriptive Statistics (point estimate, 95% CI)	PP/FAS	Missing data will not be imputed

CI = confidence interval; cLDA = constrained longitudinal data analysis; FAS = Full Analysis Set; GMC = geometric mean concentration; GMFR = geometric mean fold rise; GMT = geometric mean titer; IgG = immunoglobulin G; OPA = opsonophagocytic activity; PP = Per-protocol.

^a cLDA model with terms for time and the interaction of time-by-vaccination group.

9.6.2 Statistical Methods for Immunogenicity Analyses in Phase 2

This section describes the statistical methods that address the primary and secondary Phase 2 immunogenicity objectives. The margins of noninferiority and superiority (ie, statistically significantly greater) presented below are consistent with previous early phase comparative studies [Jackson, L. A., et al 2013].

The immunogenicity analyses will be conducted for each serotype separately.

Primary Endpoints/Hypotheses

For the common serotypes, the primary noninferiority hypotheses (H1) regarding OPA GMT levels between recipients of pPCV and PNEUMOVAXTM23 is:

$$\begin{aligned} H_0: \text{GMT}_1/\text{GMT}_2 &\leq 0.33 \text{ versus} \\ H_1: \text{GMT}_1/\text{GMT}_2 &> 0.33 \end{aligned}$$

where GMT_1 is the serotype-specific OPA GMT for the pPCV group and GMT_2 is the serotype-specific OPA GMT for the PNEUMOVAXTM23 group. A ratio of 0.33 corresponds to a 3.0-fold lower OPA GMT in the pPCV group compared with the PNEUMOVAXTM23 group. Rejecting the null hypothesis (H_0) at the 1-sided $\alpha=0.025$ level corresponds to the lower bound of the 2-sided 95% CI on the GMT ratio (pPCV/PNEUMOVAXTM23) being >0.33 and would lead to the conclusion that the OPA response to pPCV for the common serotype is noninferior to that of PNEUMOVAXTM23.

For the serotypes that are unique to pPCV, the primary superiority (ie, statistically significantly greater) hypotheses (H2) regarding OPA levels between recipients of pPCV group and PNEUMOVAXTM23 group is:

$$\begin{aligned} H_0: \text{GMT}_1/\text{GMT}_2 &\leq 1.0 \text{ versus} \\ H_1: \text{GMT}_1/\text{GMT}_2 &> 1.0 \end{aligned}$$

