9.8 Multiplicity

As described in Section 9.6.2, there are 2 types of hypothesis tests for the Phase 2 immunogenicity analysis: (1) a separate noninferiority test for each of the common serotypes between pPCV and PNEUMOVAX™23, and (2) a separate superiority (ie, statistically significantly greater) test for each of the serotypes that are unique to pPCV. This study will be considered to have met its primary immunogenicity objective if success is demonstrated for all common serotypes and all unique serotypes included in the primary immunogenicity hypotheses. The intersection-union test controls the overall type I error at the 1-sided 0.025 level within each group; therefore, no multiplicity adjustment will be required within each group [Berger, R. L. 1982]. The intersection-union test refers to the fact that the set of statistical null hypotheses to be tested can be expressed as a union, and the set of statistical alternative hypotheses as an intersection. Thus, the overall statistical null hypothesis can only be rejected if each of the set of statistical null hypotheses are rejected.

The same multiplicity strategy will be applied to the 2 secondary study hypotheses for which there is also a noninferiority hypothesis for the common serotypes between pPCV and PNEUMOVAX™23, and a superiority (ie, statistically significantly greater) hypothesis for the serotypes unique to pPCV, as measured by IgG. In this way, for the secondary hypotheses to be supported by the data, all statistical tests will have to be statistically significant. This approach controls the type I error at 0.025 (1-sided) for the set of primary hypothesis tests and separately at 0.025 (1-sided) for the set of secondary hypothesis tests.

No multiplicity adjustments will be made for the safety comparisons.

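### The Phase 2 OPA powers in Section 9.9.1 (98.7%, 99.2%, 98% overall) do not follow from the inputs listed with them; the gap is under 1 point per set and conservative.

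*Combined protocol and SAP*

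**What the plan says.** Section 9.9.1 gives four set-level powers for Phase 2. For the primary OPA hypotheses, "there is 98.7% power to declare primary noninferiority" and 99.2% power for superiority on the unique serotypes; their product is given as 98%. For the secondary IgG hypotheses, "there is 87% power for the secondary noninferiority hypothesis and 92% power for the secondary superiority", with 80% overall. Section 9.1 repeats these figures.

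The inputs stand in the same section: "Assuming 90% evaluability (approximately 225 participants per group"); "The standard deviation of natural log-transformed OPA assay and IgG results are 2.2 and 1.73, respectively"; true ratios of 1 for common serotypes, and 3 (OPA) or 2 (IgG) for unique ones. Section 9.6.2 gives the OPA margin: "A ratio of 0.33 corresponds to a 3.0-fold lower OPA GMT in the pPCV group". The IgG margin is 0.5. Under Section 9.8 every serotype in a set must pass at 1-sided 0.025.

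Two things needed to rebuild the powers are absent. The numbers of common and unique serotypes are left to the sSAP (Section 9.4.2). The rule for combining serotypes within a set is not given; Section 9.9.1 states only that the two set powers are multiplied.

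**The concern.** H1 and H3 concern the common serotypes and H2 and H4 the unique ones, so one n and one pair of counts would be expected to produce all four powers. The IgG figures fit the listed inputs with plausible counts. The OPA figures do not: they are lower than those inputs allow.

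What is at stake is traceability, not the size of the trial. These are the powers for the primary immunogenicity hypotheses, and Section 9.7.1 says the Phase 2 power and sample size assumptions will be examined after Phase 1. Whoever does that needs to know which n and which standard deviation lie behind the printed values.

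**Working it through.** **Inputs.** n = 225 per group; SD 2.2 (OPA) and 1.73 (IgG); true ratios 1 for common, 3 (OPA) and 2 (IgG) for unique (all Section 9.9.1). Allocation 1:1 (Section 6.3.1). Margins 0.33, described as 3-fold, and 0.5 (Section 9.6.2). 1-sided 0.025, all serotypes must pass (Section 9.8). PNEUMOVAX 23 has 23 serotypes (Section 2.2.3.1).

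**Stated products.** 0.987 × 0.992 = 0.979 (stated 98%) and 0.87 × 0.92 = 0.800 (stated 80%). Both agree.

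**Per-serotype power.** SE = SD × √(2/225); power = Φ(δ/SE − 1.96). I also used the noncentral t.

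- OPA: SE = 2.2 × 0.0943 = 0.2074.
  - Noninferiority, margin 0.33: δ = −ln 0.33 = 1.109; δ/SE = 5.345; failure 0.036% (t: 0.037%).
  - Superiority, or noninferiority with margin exactly 1/3: δ = ln 3 = 1.099; δ/SE = 5.297; failure 0.042% (t: 0.044%).
- IgG: SE = 1.73 × 0.0943 = 0.1631; δ = ln 2 = 0.693; δ/SE = 4.250; failure 1.10% (t: 1.13%).

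**Check that needs neither the counts nor independence.** The chance of failing a set cannot exceed k times the per-serotype failure, whatever the correlation (Bonferroni inequality).

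- H1, with all 23 PNEUMOVAX 23 serotypes counted as common: failure is at most 23 × 0.0442% = 1.02%, so power is at least 98.98% in the least favourable variant (t, margin 1/3). With margin 0.33 it is at least 99.1%. The stated 98.7% lies below this floor.
- Allowing for rounding, 98.7% means a failure of at least 1.25%. That needs k ≥ 1.25/0.0442 = 28.3, so at least 29 common serotypes; with margin 0.33 (t) it needs at least 34. There are at most 23.
- 99.2% means a failure of at least 0.75%, so k ≥ 0.75/0.0442 = 17.0, at least 17 unique serotypes. Taken alone, this is not excluded. Jointly, the two OPA figures need 29 + 17 = 46 serotypes, whereas the IgG assay for the pPCV serotypes has "3 groups of 8, 9, and 7 serotypes each", which is 24.
- Overall, with 24 serotypes in total: failure is at most 24 × 0.0442% = 1.06%, so power is at least 98.9%, against 98% stated.

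**Check assuming independence within sets** (set power = per-serotype power to the power k). Allowing for rounding, the IgG figures imply 11.8-13.1 common and 6.9-8.0 unique serotypes. Ranges below cover normal and t, and for OPA noninferiority both margins.

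| Set | Stated | 225 per group, listed SD |
|---|---|---|
| IgG, 12-13 common | 87% | 86.3-87.6% |
| IgG, 7-8 unique | 92% | 91.3-92.5% |
| OPA, 12-13 common | 98.7% | 99.4-99.6% |
| OPA, 7-8 unique | 99.2% | about 99.7% |

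The OPA product is about 99% (for example 0.9945 × 0.9966 = 0.991).

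**What would match the printed OPA values.**

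- 200 per group, SD 2.2, 12 and 7 serotypes, margin 0.33: 98.7-98.8% and 99.1-99.2%.
- 205 per group, SD 2.2, 13 and 8 serotypes, margin 1/3: 98.7% and 99.2%.
- 225 per group, SD 2.3, 13 and 8 serotypes, margin 1/3: 98.7-98.8% and 99.2%.

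At 200 per group the IgG powers with 12 and 7 serotypes would be only about 78% and 86-87%, so lowering n for both assays does not reconcile the four figures.

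**The case against.** The strongest reply is that the difference is trivial. One n and one pair of counts come within about 0.9 points of all four powers, which many would accept as reproduction. Back-solving a serotype count from a power this close to 1 is badly conditioned: a gap of 0.5 to 0.9 points more than doubles the implied count. The counts 12-13 and 7-8 also rest on independence, which the plan does not state; positive correlation would raise the counts implied by IgG. All of this stands, and it limits what may be concluded.

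It does not remove the point. A 2-point tolerance cannot discriminate near 100%. The plan prints the OPA figures to one decimal, and the bound for H1 uses neither the serotype counts nor independence. Nor does the planned model rescue the figure: the constrained longitudinal analysis also uses the Day 1 titers, which would generally raise power above the two-sample value.

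Three stronger readings are tempting and not supported:

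- **The power statement contradicts itself.** The products agree, the IgG figures fit, and the OPA figures miss by less than 1 point per set. What is shown is that the OPA figures do not follow from the listed inputs.
- **The OPA calculation used 80% evaluability.** 200 of 250 is one match among several; a larger SD at 225 does as well, and no section mentions 80%.
- **Secondary power is really below 80% because 24 serotypes will be tested.** Section 8.2.2 describes an assay format. The hypothesis sets are deferred to the sSAP, and the IgG figures themselves fit about 20 serotypes.

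**Conclusion.** The point holds in a narrow form. At 225 per group, SD 2.2 and the stated ratios, margin and alpha, H1 power is at least about 99.0% whatever the correlation, so 98.7% is wrong for those inputs. The 99.2% is excluded only jointly with 98.7%, or with the counts that the IgG figures imply under independence. On those counts the OPA powers are understated by about 0.7-0.9 points (H1) and 0.5 points (H2), and the overall figure by a little over 1 point. On the failure scale, H1 is stated as 1.3% against about 0.4-0.6%.

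The error is conservative. Enrolment, analysis, success criteria and the conclusion of adequate power are unaffected, and nothing here suggests that the trial is underpowered. Whether the printed power, the OPA n or the OPA SD is the wrong figure cannot be settled from the documents. The check takes the listed SDs as those of the Day 30 log results in a plain two-sample comparison. This is a minor correction.

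**What to change.** Recompute the four powers and the two products from one n, one SD per assay and one pair of serotype counts. State those counts in Section 9.9.1, or as a working assumption if the sets stay in the sSAP, and state how serotypes are combined within a set (independence or an assumed correlation). Then do one of two things:

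- keep 225 per group and SD 2.2, and restate OPA power as about 99.5% and 99.7%, overall about 99% (under independence, with the counts above); or
- if a different n or SD was used for OPA, print that one.

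Make the same change in Section 9.1. The cost is one re-run of the power calculation and a text correction; enrolment does not change.

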9.9.2 Safety Analyses

For safety comparisons, all participants are expected to be evaluable.

In Phase 1, if no SAEs are observed among the 30 participants in each vaccination group, this study provides 68.7% confidence that the true SAE rate is <1.2% (1 out of every 83 participants). In Phase 2, if no SAEs are observed among the 250 participants in each vaccination group, this study provides 97.9% confidence that the true SAE rate is <1.5% (1 out of every 67 participants).

The probability of observing at least 1 SAE in this study depends on the number of participants enrolled and the incidence rate of SAEs in the general population. In Phase 2, if the incidence rate of an SAE is 1 of every 143 recipients of the vaccine (0.7%), then there is an 80% chance of observing at least 1 such SAE among 250 participants in the pPCV group. If the incidence rate is 1 of every 332 recipients of the vaccine (0.3%), then there is a 50% chance of observing at least 1 SAE among 250 participants in the pPCV group.

For the Phase 2 safety comparisons, risk differences between the 2 vaccination groups that could be detected with an 80% probability are summarized in [Table 10](#) for a variety of hypothetical true incidence rates. These calculations assume that there are 250 evaluable participants in both groups and are based on a 2-sided significance level of $\alpha=0.05$. No multiplicity adjustments were made in these calculations.

Table 10 Differences in the Incidence of Adverse Event Rates Between the 2 Vaccination Groups in Phase 2 That Can be Detected With Approximately 80% Probability

Incidence of Adverse Event		Risk Difference
pPCV (%)	PNEUMOVAX™23 (%)	Percentage Points
3.6	0.1	3.5
7.6	2.0	5.6
12.3	5.0	7.3
19.2	10.0	9.2
25.5	15.0	10.5
31.4	20.0	11.4
42.5	30.0	12.5

The incidence rates for each vaccination group are hypothetical and do not represent actual adverse events in either group.

The incidences assume a 2-sided 5% alpha level with 250 participants in each group. No multiplicity adjustments were made.

The calculations are based on an asymptotic method proposed by Farrington and Manning [Farrington, C. P. 1990].

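### Phase 1 SAE precision statement is wrong: zero SAEs in 30 participants gives 30.4% confidence that the rate is below 1.2%, not 68.7%

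*Combined protocol and SAP*

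**What the plan says.** Section 9.9.1 sets the size of Phase 1: "In Phase 1, approximately 90 participants will be enrolled, with approximately 30 participants in each of the 3 vaccination groups". Section 9.9.2 opens the safety calculations by making no deduction for dropout: "For safety comparisons, all participants are expected to be evaluable". It then gives the one Phase 1 figure, conditional on a clean result with no SAEs "among the 30 participants in each vaccination group, this study provides 68.7% confidence that the true SAE rate is <1.2"%, a bound it also expresses as 1 in 83.

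The sentence that follows makes the same kind of statement for Phase 2, with 250 participants per group: "this study provides 97.9% confidence that the true SAE rate is <1.5% (1 out of every 67 participants"). Everything after that in Section 9.9.2, including Table 10, concerns Phase 2.

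**The concern.** Thirty event-free participants say little about a rate near 1%. At a true rate of 1.2% the expected number of SAEs in a group of 30 is 30 × 0.012 = 0.36, so a clean group would be the usual result even if the rate were exactly at the bound. A confidence of nearly 69% is not plausible on that footing.

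Sections 1.1 and 3 make safety the only primary objective of Phase 1, with vaccine-related SAEs among its primary endpoints. Section 2.2.2 says that no clinical study of this vaccine came before, and Section 9.6 plans estimation only for Phase 1. A precision statement is therefore the only quantitative account of what 30 participants per group can show about SAEs, and this is the only one given. Phase 1 data go to the siDMC and the study team for the decision on Phase 2 (Sections 4.1 and 9.7.1). A reader who relies on the sentence would credit a clean group with more than twice the assurance it provides.

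**Working it through.** **Inputs**, all from Section 9.9.2, with the group size confirmed in Section 9.9.1:

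- n = 30 per Phase 1 vaccination group, all evaluable for safety
- observed SAEs = 0
- bound p = 1.2%, also given as 1 in 83 (1.205%)
- stated confidence = 68.7%

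**Formula.** If the true rate is p, the chance of no events in n participants is (1 − p)^n. After observing none, the exact one-sided confidence that the rate is below p is 1 − (1 − p)^n.

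**Check of the method on the Phase 2 sentence** (n = 250, p = 1.5%): 1 − 0.985^250 = 97.7%, against 97.9% stated. The difference is 0.2 points, so this is evidently the kind of calculation intended.

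**Phase 1 as stated:**

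- p = 1.2%: 1 − 0.988^30 = 1 − 0.696 = **30.4%**
- p = 1/83: 1 − (82/83)^30 = **30.5%**
- gap: 68.7 − 30.4 = 38.3 percentage points; ratio 68.7/30.4 = 2.3

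**Attempts to recover 68.7%:**

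| Reading | Confidence |
|---|---|
| n = 30, p from 1.15% to 1.249% (rounds to 1.2%) | 29.3% to 31.4% |
| n = 30, Poisson, p = 1.2% | 30.2% |
| n = 30, Bayes with uniform prior | 31.2% |
| n = 30, Bayes with Jeffreys prior | 60.7% |
| n = 30, Wilson, one-sided / two-sided | 72.7% / 45.4% |
| n = 60 (both pPCV groups), exact | 51.5% |
| n = 90 (all of Phase 1), exact | 66.3% (66.4% at 1/83) |

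None of these gives the stated figure.

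**Solving for each quantity in turn:**

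- n needed for 68.7% at 1.2%: ln(0.313)/ln(0.988) = 96.2 (95.8 at 1/83). No Phase 1 group or pool has that many.
- Bound supported at 68.7% with n = 30: 1 − 0.313^(1/30) = 3.8%, about 1 in 26 and 3.8/1.2 = 3.2 times the stated bound.
- Bound supported at 68.7% with n = 90: 1 − 0.313^(1/90) = 1.28%, about 1 in 78, which is neither 1.2% nor 1 in 83.
- One-sided 95% upper bound for 0/30: 1 − 0.05^(1/30) = 9.5%, about 1 in 10.5.

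**The case against.** **The sentence may mean no SAEs in any group, so that all 90 participants count.** This is the nearest pooled reading with the exact formula, but it gives 66.3% to 66.4%. It also sits badly with a sentence framed by vaccination group, and it would use 30 comparator recipients as evidence about the new vaccine. It does not stand.

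**The figure drives nothing.** This is true. No test, sample size, stopping rule or decision threshold uses it. The Phase 2 decision rests on observed data, and SAEs will be reported as Tier 2 events with confidence intervals calculated from those data (Section 9.6.3), so the reported results will not inherit the error. That limits the consequences. It does not replace the statement, because the Tier 2 intervals are for between-group differences and not for the rate in one group.

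**The documents do not show which number is wrong.** This is fair. With n = 30, either the confidence should be 30.4% for the stated bound, or the bound should be 3.8% for the stated confidence. The stated figures cannot stand together, and both repairs are less favourable than the current text.

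**Other figures in Section 9.9.2 also miss.** With 250 participants, the chance of seeing at least one SAE is 1 − (142/143)^250 = 82.7% where 80% is stated, and 1 − (331/332)^250 = 53.0% where 50% is stated. These gaps are about 3 points and understate the chance of detection. They are a reason to recalculate the whole section, not a defence of the Phase 1 figure.

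**Conclusion.** The concern holds. On the plan's own inputs (zero SAEs, 30 participants per group, all evaluable), the confidence that the true SAE rate is below 1.2% is 30.4%. The plan states 68.7%, which is 38 points too high and more than double. The result rests on the exact binomial calculation with independent participants, which comes within 0.2 points of the Phase 2 companion figure. The other methods tried at n = 30, and the pooled group sizes under the exact formula, do not give 68.7% either. The implied sample size of about 96 might suggest a figure carried over from another design, but the documents do not show how the error arose and the conclusion does not depend on it.

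The error lies in a descriptive statement about a primary safety endpoint. It affects how a clean Phase 1 group is understood, not any test or sample size.

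**What to change.** Replace the Phase 1 sentence in Section 9.9.2 with wording such as: *With no SAEs among the 30 participants in a vaccination group, there is 30.4% confidence that the true SAE rate in that group is below 1.2%.*

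A conventional bound would inform the reader better and could be added or used instead: *there is 95% confidence that the true SAE rate is below 9.5% (about 1 in 10.5)*. That is a choice of presentation. What must be corrected is the mismatch between sample size, bound and confidence.

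The Phase 2 detection probabilities in the same section should be recalculated at 250 participants in the same revision. The cost is a small text change and a less favourable Phase 1 figure, with no change to sample size, analyses or conduct.

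### The Phase 2 safety detectability figures (Table 10 and both at-least-one-SAE statements) do not follow from the stated 250 per group; all of them fit 230

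*Combined protocol and SAP*

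**What the plan says.** Section 9.9.2 (Safety Analyses) takes full evaluability as its premise: "For safety comparisons, all participants are expected to be evaluable". Section 9.9.1 sets the Phase 2 size at "approximately 250 participants in each of the 2 vaccination groups".

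Four kinds of Phase 2 statement follow in Section 9.9.2, each tied to 250:

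- With an SAE rate of 1 in 143 (0.7%), "then there is an 80% chance of observing at least 1 such SAE among 250 participants in the pPCV group".
- With a rate of 1 in 332 (0.3%), "then there is a 50% chance of observing at least 1 SAE among 250 participants in the pPCV group".
- Table 10 lists "risk differences between the 2 vaccination groups that could be detected with an 80% probability". The text introducing it says "These calculations assume that there are 250 evaluable participants in both groups and are based on a 2-sided significance level" (0.05), and its footnote repeats this: "The incidences assume a 2-sided 5% alpha level with 250 participants in each group". The method named is Farrington-Manning.
- If no SAE is seen among 250, "this study provides 97.9% confidence that the true SAE rate is <1.5"%.

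**The concern.** Sample size, alpha, target probability and method are all given, so each figure can be checked. The at-least-one-SAE statements involve only a binomial probability, and neither comes out at 250. Table 10 is off in the same direction in every row. That pattern points to a different sample size in the calculation, not to rounding.

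Safety is a primary Phase 2 objective, and Section 9.9.2 is where the plan says what the trial can detect for safety. A reader who checks the figures finds that they and the stated sample size cannot both be right, and cannot tell which one the sponsor means.

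**Working it through.** **Inputs (Section 9.9.2).** n = 250 per group, 1:1; two-sided alpha 0.05; 80% probability; SAE rates 1/143 and 1/332; Table 10 rates as printed.

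**1. At least one SAE.** P = 1 − (1 − p)^n.

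| Rate | Plan | n = 250 | n = 230 |
|---|---|---|---|
| 1/143 | 80% | 1 − (142/143)^250 = 82.7% | 80.1% |
| 1/332 | 50% | 1 − (331/332)^250 = 53.0% | 50.0% |

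Solving for the rate, p = 1 − (1 − P)^(1/n):

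- n = 250: 1 − 0.2^(1/250) = 0.00642, or 1 in 155.8; 1 − 0.5^(1/250) = 0.00277, or 1 in 361.2.
- n = 230: 1 in 143.4 and 1 in 332.3, which round to the printed 143 and 332.
- n = 225 (the 90% evaluability figure for immunogenicity in Section 9.9.1): 1 in 140.3 and 1 in 325.1.

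**2. Table 10.** With a null difference of zero and equal groups, the Farrington-Manning calculation is the pooled-variance formula:

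power = Φ{ [ |p1 − p2|·√n − 1.96·√(2p̄(1 − p̄)) ] / √(p1(1 − p1) + p2(1 − p2)) }, with p̄ = (p1 + p2)/2.

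Worked row, 19.2% against 10.0%: p̄ = 0.146, √(2p̄(1 − p̄)) = 0.4994, and the denominator is 0.4951.

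- n = 230: (0.092 × 15.166 − 1.96 × 0.4994)/0.4951 = 0.841, so power is 80.0%.
- n = 250: (0.092 × 15.811 − 1.96 × 0.4994)/0.4951 = 0.961, so power is 83.2%.

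All rows, with the pPCV rate solved for 80% power:

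| PNEUMOVAX 23 (%) | Printed pPCV (%) | n = 230 | n = 250 | Power of printed row at 250 | Difference printed | Difference at 250 |
|---|---|---|---|---|---|---|
| 0.1 | 3.6 | 3.62 | 3.36 | 82.95% | 3.5 | 3.3 |
| 2.0 | 7.6 | 7.56 | 7.25 | 83.58% | 5.6 | 5.3 |
| 5.0 | 12.3 | 12.33 | 11.97 | 82.93% | 7.3 | 7.0 |
| 10.0 | 19.2 | 19.20 | 18.77 | 83.18% | 9.2 | 8.8 |
| 15.0 | 25.5 | 25.47 | 25.00 | 83.39% | 10.5 | 10.0 |
| 20.0 | 31.4 | 31.39 | 30.89 | 83.27% | 11.4 | 10.9 |
| 30.0 | 42.5 | 42.53 | 42.00 | 83.03% | 12.5 | 12.0 |

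At 230 all seven rows match to the printed decimal; at 250 none does. The n that gives exactly 80% power at the printed rates runs from 227.6 to 231.6. Among whole numbers from 215 to 260, only 230 matches all seven rows.

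**3. Other explanations tried.**

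- n = 225, pooled: 3.69, 7.64, 12.43, 19.32, 25.60, 31.52, 42.67%. One row matches.
- n = 250, unpooled variance: 3.33% to 41.93%, further from the printed values.
- n = 250, continuity correction: 4.07, 7.79, 12.45, 19.23, 25.44, 31.32, 42.41%. This does not fit the table as a whole.
- Unpooled variance at n = 228 comes close for Table 10 alone, but n = 228 gives 1 in 329 for the 50% statement, not 1 in 332.

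**4. Zero-SAE statement.** 1 − 0.985^250 = 97.7%; 1 − 0.985^230 = 96.9%. The printed 97.9% is neither. It is close to the value at 250, so this sentence does not share the 230 basis.

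**The case against.** The best case for leaving this alone is that little depends on it. The plan tests no safety hypothesis and defines no Tier 1 events, and Section 9.6.3 treats the Tier 2 intervals as descriptive. The error is also conservative: with 250 per group the trial is slightly more sensitive than claimed. The Table 10 title says approximately 80%, and Section 9.9.1 says approximately 250. The number 230 is not in the documents, and 250 is the only safety sample size a reader meets.

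Much of this stands. The consequence is modest, no analysis or design decision changes, and 230 is a back-calculation. But the word approximately does not cover a shift of about 3 points of power, in the same direction, in all seven rows, which disappears at a single n. The two SAE sentences give 80% and 50% without qualification and show the same shift. Because 250 is the only stated basis, recomputing at 250 is the more natural correction. The zero-SAE figure is a separate discrepancy of 0.2 points and is not evidence for 230.

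**Conclusion.** The concern holds. Nine printed results (seven Table 10 rows and two SAE rates) do not follow from the stated 250 per group. At 250, the 80% and 50% SAE rates are 1 in 156 (0.64%) and 1 in 361 (0.28%), against the printed 1 in 143 and 1 in 332. The detectable differences are 3.3 to 12.0 points, against the printed 3.5 to 12.5.

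The mismatch needs no assumption beyond the plan's own inputs and, for Table 10, the pooled-variance form of the named method. That 230 was the value used is inferred, but two separate calculations agree on it. The plan understates its own sensitivity, so the direction is harmless. Immunogenicity sample size and power, which rest on 225 evaluable per group, are untouched.

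**What to change.** Recompute Section 9.9.2 at 250 per group:

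- 80% chance of at least one SAE: 1 in 156 (0.64%).
- 50% chance: 1 in 361 (0.28%).
- Zero-SAE confidence for a rate below 1.5%: 97.7%.
- Table 10 pPCV rates: 3.4, 7.3, 12.0, 18.8, 25.0, 30.9 and 42.0%, with differences of 3.3, 5.3, 7.0, 8.8, 10.0, 10.9 and 12.0 points.

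If 230 evaluable per group was the intended assumption, say so in the text and the Table 10 footnote, and reconcile it with the statement that all participants are evaluable for safety. In that case the zero-SAE figure at 230 would be 96.9%.

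The cost is a text and table correction in one section. Sample size, design and analysis do not change.
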